## **11. STATISTICS**

### **11.1. General Considerations**

A separate statistical analysis plan will provide technical details of the statistical analyses to be performed, in addition to the specifications in this protocol.

### **11.2. Sample Size**

For this group with critical disease, the null hypothesis is that 50% of subjects will survive for 28 days. The alternative hypothesis is that at least 90% of subjects receiving GC4419 will survive for 28 days compared with the control survival of 50%. A sample size of 50 subjects, 25 in each group, is expected to provide approximately 80% power to detect this difference with a two-sided alpha of 0.05.

### **11.3. Randomization and Stratification**

Eligible subjects will be randomized 1:1 to the two treatment arms using a permuted block randomization schedule. Randomization will be stratified by age (<60 versus  $\geq$ 60 years).

### **11.4. Analysis Populations**

All randomized subjects who receive at least one dose of blinded GC4419/placebo will be included in the population to be analyzed for safety and efficacy.

## **11.5. Definition of Endpoints**

### **11.5.1. Primary Endpoint**

- The primary endpoint is 28-day mortality

### **11.5.2. Secondary Efficacy Endpoints**

- safety of avasopasem
- frequency of successful ventilator weaning
- days alive and intensive care-free
- days alive and ventilator-free
- days alive with minimum  $\text{PaO}_2/\text{FiO}_2 \geq 300\text{mmHg}$
- days alive and without vasopressor/catecholamine support
- incidence of mean arterial pressure  $< 65 \text{ mmHg}$  on optimized vasopressor therapy
- days alive with a SOFA score of 6 or less
- percentage of subjects with an increase in mean arterial pressure of 10 mm Hg or more at the end of more than one infusion of GC4419

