Based on case reports from the current COVID-19 outbreak, three additional nonclinical findings may also be important in subsets of patients. First, based on the understanding that in the hyperinflammatory state,  $O_2^{\bullet-}$  can initiate the auto-oxidation of catecholamines, leading to self-perpetuating refractory hypotension, the MnPAM dismutase mimetics have been shown in multiple models to restore response to vasopressor therapy and maintain mean arterial blood pressure [36-38]. It is unclear how broadly refractory hypotension is an issue for critically ill COVID-19 patients, however renal failure does seem to be a substantial issue. While renal failure may be due to compromised circulation (perhaps stemming from refractory hypotension), acute kidney injury has also been linked directly to  $O_2^{\bullet-}$  and such injury is reduced by the MnPAM dismutase mimetics in models of direct injury by cisplatin and of the zymosan-induced inflammatory response [30,34]. In addition, in a randomized Phase 2 setting, post hoc analysis suggests that GC4419 reduces chronic kidney disease in cisplatin-treated patients [57]. Finally, analogous to lung injury models discussed above, in myocardial injury models, GC4403 reduced  $O_2^{\bullet-}$ , neutrophil infiltrate, lipid peroxidation and myocardial damage, while significantly improving cardiac function post-ischemia/reperfusion, transplant or hyperglycemia [58-61], suggesting that a MnPAM dismutase mimetic might also reduce cardiac myopathy seen in some

critically ill COVID-19 patients. Further, MnSOD overexpression reverses pulmonary hypertension (PAH) in the fawn-hooded rat [62]. In alignment with that MnPAM dismutase mimetics have been shown to reduce PAH in hypoxic piglet and bleomycin rat models [63-66], which could also be a beneficial activity in patients with myocardial injury. Thus, beyond treating or preventing ARDS, in critically ill COVID-19 patients may offer help with refractory hypertension, renal impairment and heart failure co-morbidities.

While it can be debated what the best animal models of ARDS or of critically ill COVID-19 patients are, the nonclinical data above argue strongly for assessing the MnPAM dismutase mimetics in this indication, as well as for protection of other organs targeted by cytokine storm.

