### 5.2. Secondary Objectives

The following secondary objectives will be assessed through a 28-day period to align with the primary objective:

- To assess the safety of avasopasem in the study population
- To evaluate the frequency of successful ventilator weaning
- To evaluate the number of days alive and intensive care-free
- To evaluate the number of days alive and ventilator-free
- To evaluate the number of days of minimum SpO2/FIO2 ratio or PaO2/FIO2 > 300
- To evaluate the number of days alive without vasopressor/catecholamine support
- To evaluate the incidence of mean arterial pressure < 65 mmHg on optimized vasopressor therapy
- To evaluate the number of days alive with a SOFA score of 6 or less
- To evaluate the percentage of subjects with an increase in mean arterial pressure of 10 mm Hg or more at the end of more than one infusion of GC4419

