## **9. TOXICITY MANAGEMENT**

### **9.1. Anticipated toxicities of GC4419**

Based on the drug's mechanism of action, adverse effects anticipated with GC4419 are attributable to transient potentiation of nitric oxide. Clinical results with GC4419 to date are consistent with this. These effects have been IV infusion related and transient, typically with onset during or at the end of infusion, resolving within 1-2 hours of cessation of GC4419 administration. At the dose and schedule planned in this trial, these effects may include mild hypotension, postural lightheadedness/presyncope, and perioral/facial tingling or paresthesia. Mild nausea and vomiting have also been observed in human subjects receiving GC4419.

See the investigator's brochure for additional details.

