### **9.2. Dose Delays and Dose Modifications for Toxicity**

*For any given subject, study drug infusions should not begin if the subject's mean arterial pressure (MAP) is less than 65 mmHg.*

For any given subject, hold blinded GC4419/placebo and reduce by 25% (from the initial dose) for all future infusions if:

- During infusion or within 1 hour of completing infusion, the subject experiences an acute decrease in systolic blood pressure requiring bolus fluid resuscitation OR requiring initiation of vasopressor therapy OR increased vasopressor therapy. Hold GC4419/placebo until the dose of vasopressor therapy is stable and bolus fluid resuscitation is not required.
- The subject develops serum creatinine  $> 5$  mg/dL. Hold GC4419/placebo until the creatinine is  $=< 5$  mg/dL.
- The subject develops serum total bilirubin  $> 6$  mg/dL, or AST or ALT  $> 10$  times upper limit of normal. Hold GC4419/placebo until the parameters in question are below these levels.
- The subject experiences a serious or severe adverse event considered by the investigator to be related or possibly related to blinded GC4419/placebo. Hold GC4419/placebo until the event is no longer serious or severe.

Up to two such dose reductions for a cumulative 50% from the initial dose of GC4419/placebo will be permitted for a given subject. If a subject cannot tolerate GC4419/placebo infusion after a 50% dose reduction, all dosing with GC4419/placebo for that subject will be discontinued.

Patients unable to tolerate GC4419/placebo must discontinue treatment with GC4419/placebo but should continue with other protocol assessments at the discretion of the treating investigator and with the ongoing consent of the subject.

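### The secondary MAP-rise endpoint names no reference reading and sets no condition on vasopressors or fluids, so a rise produced by rescue during the infusion can count as a response

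*Combined protocol and SAP*

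**What the plan says.** The endpoint appears in the Synopsis objectives, in Section 5.2 ("an increase in mean arterial pressure of 10 mm Hg or more at the end of more than one infusion of GC4419") and in Section 11.5.2 ("an increase in mean arterial pressure of 10 mm Hg or more at the end of more than one infusion"). None of the three names the reference reading. None mentions vasopressor dose or fluids, and none says how an infusion with a change in either is scored. Read literally, the wording also covers only GC4419 infusions, not placebo infusions.

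A neighbouring endpoint in Section 11.5.2, the incidence of MAP below 65 mmHg, is qualified by "on optimized vasopressor therapy". The MAP-rise endpoint carries no such qualifier.

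Section 9.1 says of anticipated toxicity that "these effects may include mild hypotension, postural lightheadedness/presyncope, and perioral/facial tingling or paresthesia". Section 9.2 (repeated in the Synopsis) makes an "acute decrease in systolic blood pressure requiring bolus fluid resuscitation OR requiring initiation of vasopressor therapy OR increased vasopressor therapy", during infusion or within 1 hour of its completion, a trigger to hold and reduce study drug. It does not link that event to the endpoint.

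Appendix 1 schedules MAP before each infusion, every 30 minutes during it, at its end, and at 1, 2 and 4 hours after (footnote 4). Vasopressor requirements are recorded at screening and then every 12 hours while on vasopressors (footnote 5). Section 11.7.2 makes all secondary analyses descriptive. Section 11.1 leaves technical details to a separate analysis plan; the available document contains no text from it.

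**The concern.** In this population MAP is a treated variable. The scientific case for the endpoint is in Section 4.1.3, where the drug class is said to "restore response to vasopressor therapy and maintain mean arterial blood pressure" in animal models. A raw MAP rise with uncontrolled vasopressor dose cannot separate that effect from a larger vasopressor dose or a fluid bolus.

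Suppose pressure falls during an infusion, staff raise the vasopressor, and MAP ends 10 mmHg above the reference. Under Section 9.2 that infusion contained a toxicity event; under Section 11.5.2 it can be one of the two infusions that make the subject a responder. At stake is the meaning of the responder percentage in each arm and, if rescue is more common on one arm, the comparison between arms.

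**Working it through.** The protocol states no figure for this endpoint, so there is none to reproduce. The calculation below is illustrative and all its rates are assumed.

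**Inputs from the protocol**
- Infusions: every 12 hours for 7 days (Section 6.2), so up to 14 per subject.
- Response: a qualifying rise in more than one infusion, so at least 2 (Section 11.5.2).
- Dose rule: up to two reductions, then discontinuation if study drug is still not tolerated (Section 9.2). This is modelled as dosing stopping at the third rescue event.

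**Assumed inputs**
- e, the chance of rescue (vasopressor start or increase, or bolus) in an infusion: 10% on placebo, 20% on GC4419.
- r, the chance that MAP ends at least 10 mmHg above the reference after rescue: 10%, 30% or 50%.
- Independent infusions, no drug benefit, and no rises other than rescue-driven ones.

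**Formula.** With K rescue events in 14 infusions, K ~ Binomial(14, e), capped at 3:

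P(false responder) = P(K = 2) × r² + P(K ≥ 3) × (3r² − 2r³)

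- e = 10%: P(K = 2) = 0.2570, P(K ≥ 3) = 0.1584
- e = 20%: P(K = 2) = 0.2501, P(K ≥ 3) = 0.5519

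For r = 50%, the two weights are 0.25 and 0.75 − 0.25 = 0.50:
- placebo: 0.2570 × 0.25 + 0.1584 × 0.50 = 0.143
- GC4419: 0.2501 × 0.25 + 0.5519 × 0.50 = 0.339

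| r | Placebo (e = 10%) | GC4419 (e = 20%) | False difference |
|---|---|---|---|
| 10% | 0.7% | 1.8% | 1 point |
| 30% | 5.7% | 14.2% | 8 points |
| 50% | 14.3% | 33.9% | 20 points |

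If e is the same in both arms, each row's difference is zero. Both rates are then inflated, but equally. If each hold also skips the next two infusions, the r = 50% row falls to about 10% against 26%, or 16 points.

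**What conditioning does.** Take the r = 50% case as per-infusion rates of rescue-driven rises: 20% × 50% = 10% on GC4419 and 10% × 50% = 5% on placebo. Add rises without rescue in 5% of infusions in each arm, and ignore the stopping rule. With q the combined rate per infusion, P(at least 2 of 14) = 1 − (1 − q)¹⁴ − 14q(1 − q)¹³.
- As written, GC4419: q = 1 − 0.95 × 0.90 = 0.145, giving 62.4%.
- As written, placebo: q = 1 − 0.95 × 0.95 = 0.0975, giving 40.2%, a false difference of 22 points.
- Counting only rises without rescue: q = 0.05, giving 15.3% in both arms.

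**The case against.** **The protocol is silent rather than explicit.** No sentence says that a rescued rise is a success, and a separate analysis plan could add a rule. That is fair, and it is why the point is that such a rise can count. But the definition sits in the protocol, has no exclusion, and would count the infusion if applied as it stands.

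**The overlap with Section 9.2 is narrow.** Rescue back to the starting pressure scores nothing if the pre-infusion reading is the reference. An infusion should not begin below MAP 65 mmHg, so MAP would have to end at 75 mmHg or more, and this must happen at least twice. A held infusion may have no ordinary end reading, later doses are reduced, and the 3-hour infusion was chosen to limit hypotension that the protocol expects to be mild. All of this argues for low r and e, where the false difference is near 1 point. It does not remove the gap, because the reference is unstated and the scoring of held infusions is not given.

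**The direction is not fixed.** A reader might infer that the endpoint is biased towards GC4419. The documents do not support that. Rescue also occurs on placebo, and no rates are given. Anticipated infusion hypotension makes more rescue on GC4419 plausible, no more. There is also an opposite error: if GC4419 restores vasopressor response, staff may wean vasopressors while MAP stays flat, and real benefit scores as non-response.

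**A rise after a vasopressor increase may itself be the hypothesised effect.** This stands. Excluding such infusions discards some signal, so the unconditioned rate should be shown as well.

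**Rescue is visible elsewhere**, in vasopressor-free days, adverse event tables and vital signs. True, but none of these tells the reader which MAP responders were rescued.

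**Conclusion.** The point holds as a defect of definition. With no reference reading and no vasopressor or fluid condition, a qualifying rise cannot be attributed to study drug, and an infusion handled as toxicity under Section 9.2 can also count towards response.

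A false difference in favour of GC4419 arises only if rescue is more frequent on GC4419. If rescue doubles from 10% to 20% of infusions, it is about 1, 8 or 20 points for r of 10%, 30% or 50%. The 20-point figure needs both the doubling and the top value of r, and should not be quoted alone. None of these rates comes from the documents.

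A reader might also infer that the trial's main conclusion is at risk. It is not: this is one of nine secondary items, analysed descriptively, and the primary mortality comparison, its type I error rate and the sample size do not depend on it. The reason to act is that the percentage will be tabulated as efficacy and could be read as haemodynamic benefit.

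**What to change.** In the Synopsis, Section 5.2 and Section 11.5.2, define response per infusion, for GC4419 and placebo alike: MAP rises by at least 10 mmHg from the pre-infusion reading to the end-of-infusion reading, with no vasopressor start or increase and no fluid bolus between those two readings. A subject is a responder if more than one infusion qualifies.

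Do not add a rule that every Section 9.2 event is a non-response. That window runs to 1 hour after the infusion, so an event after the end reading would cancel a clean rise.

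Add one yes/no CRF field per infusion: vasopressor started or increased, or bolus given, between the two readings. Recording every 12 hours may miss a change inside a 3-hour infusion, and Section 9.2 events cover only changes that follow an acute systolic fall, so data already planned do not fill this gap.

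Tabulate the unconditioned responder rate by arm alongside, as a sensitivity result.

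The cost is one CRF field and a revised endpoint sentence in three places. Some true rises that coincide with a vasopressor increase will not count in the main version; the sensitivity result shows how many subjects that affects. Benefit expressed as vasopressor weaning at a flat MAP is still not captured. No dose, hold or rescue rule changes.

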### **11.5.3. Exploratory Endpoints**

- Levels of circulating cytokines IL-6, TNF-alpha, IL-1 beta, IL-10
- SARS-CoV-2 viral load
- Plasma exposure to GC4419
- Lung compliance to be calculated from clinical data for exploratory purposes

## **11.6. Safety Analysis**

Adverse events will be grouped by system organ class, high level term, and preferred term according to the Medical Dictionary for Regulatory Activities (MedDRA) dictionary. Incidence by subject will be tabulated for all treatment emergent, serious, severe, and treatment-related AEs. Detailed listings will be provided for all SAEs, deaths, and withdrawals due to AEs.

Laboratory measurements, vital signs, and ECG parameters will be summarized by treatment group at each of the protocol specified time points.

Further details will be provided in the trial's statistical analysis plan.

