### **10.3. ADVERSE EVENTS AND SERIOUS ADVERSE EVENTS**

Adverse Events and Serious Adverse Events will be assessed daily during hospitalization and weekly after hospital discharge, for a total of 6 weeks after day 1 and encompassing at least 30 days after end of GC4419/placebo dosing (experimental arm subjects). Post-treatment AE assessments may be done on an outpatient basis for subjects who are discharged from the hospital.

The investigator is responsible for the detection and documentation of events meeting the criteria and definition of an AE or SAE as provided in this protocol. Throughout the study, AEs will be recorded in the source documents and on the appropriate pages of the CRF regardless of whether the AEs are considered related to GC4419/placebo. To avoid confusion, the AE should be recorded in standard medical terminology.

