### **10.8. Follow-up of AEs and SAEs**

After the initial AE/SAE report, the investigator is required to proactively follow each patient and provide further information on the patient's condition. The investigator will ensure that follow-up includes any supplemental investigations as may be indicated to elucidate the nature and/or causality of the AE or SAE. This may include additional laboratory tests or investigations, or consultation with other health care professionals.

Non-serious AEs that have not resolved by the end of the prescribed Follow-up Period will be considered ongoing, and marked as such in the CRF. All SAEs will be followed until they resolve, or a new baseline is established, at which point the appropriate CRF page(s) or SAE Report Form(s) will be updated.

Routine collection of AEs will stop 30 days after the end of treatment.

As reasonably requested by the Sponsor, the investigator will perform or arrange for the conduct of supplemental measurements and/or evaluations to elucidate as fully as possible the nature and/or causality of the AE or SAE. If a patient dies during participation in the study or during a recognized follow-up period, Galera Therapeutics, Inc. will be provided with a copy of any post-mortem findings, including histopathology.

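### Section 11.6 compares AEs as crude incidence by subject over 5 to 6 weeks with no stated allowance for unequal survival, so the non-fatal AE tables mix toxicity with time alive

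*Combined protocol and SAP*

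**What the plan says.** Section 11.6 plans that "Incidence by subject will be tabulated for all treatment emergent, serious, severe, and treatment-related AEs", with listings of SAEs, deaths and withdrawals due to AEs. Under Section 11.4 the denominator is every randomized subject who received at least one dose.

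The collection window is given in two ways. Section 10.3 has assessment "for a total of 6 weeks after day 1 and encompassing at least 30 days after end of GC4419/placebo dosing", which is Day 42. Section 10.8 says "Routine collection of AEs will stop 30 days after the end of treatment", which is about Day 37 after seven dosing days.

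The power calculation in Section 11.2 uses an alternative under which "at least 90% of subjects receiving GC4419 will survive for 28 days compared with the control survival of 50" (per cent).

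Section 11.6 names no fixed risk window, no rate per time at risk and no handling of death in the AE tables. Sections 11.1 and 11.6 both defer detail to a separate SAP, whose text is not among the documents.

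**The concern.** Incidence by subject is a fair comparison when both arms are observed at risk for about the same time. Here the trial is powered on a large survival difference, and the AE window is five to six times the dosing period. If the drug works, its recipients have more days in which a non-fatal event can be recorded. If it kills, they have fewer. Either way the percentage reflects survival as well as toxicity.

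This matters because the protocol describes the study as a first assessment of the safety of GC4419 in this population (Synopsis rationale; Section 5.1.1). Serious or severe AEs also feed the DMC's judgement of unacceptable risk (Synopsis; Section 14.4).

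**Working it through.** **Plan's own figure.** With p = 0.50 and 0.90, n = 25 per arm and two-sided alpha 0.05, the continuity-corrected two-proportion power is Φ[(0.40 − 1/25 − 1.96·√(2·0.7·0.3/25)) / √((0.25 + 0.09)/25)] = Φ[(0.36 − 0.254)/0.1166] = Φ(0.909) = 81.8%. This agrees with the stated figure of about 80%, so 50% and 90% are the survival rates behind the design.

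**Inputs.**
- 28-day survival S: 50% on placebo, 90% on GC4419 (Section 11.2).
- Window T: 37 days (Section 10.8) or 42 days (Section 10.3).
- Hazard h of a first non-fatal AE, equal in both arms: not in the documents. Assumed 0.02 per day, with a range shown.
- Constant death hazard: an assumption, varied below.

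**Formulas.** Death hazard m = −ln(S)/28, which is 0.02476 (placebo) and 0.00376 (GC4419) per day. Mean days alive = (1 − e^(−mT))/m. Crude incidence = h/(h + m) × (1 − e^(−(h+m)T)).

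**Time at risk.** GC4419 against placebo: 34.5 against 24.2 days to Day 37, and 38.8 against 26.1 days to Day 42 (ratio 1.49).

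**Incidence at h = 0.02, T = 42.**
- Placebo: 0.02/0.04476 × (1 − e^(−1.880)) = 0.447 × 0.847 = 37.9%.
- GC4419: 0.02/0.02376 × (1 − e^(−0.998)) = 0.842 × 0.631 = 53.1%.
- Gap: 15.3 points before rounding. The same steps at T = 37 give 49.2% against 36.2%, a gap of 13.1.

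| h per day | Gap, Day 37 | Gap, Day 42 |
|---|---|---|
| 0.005 | 4.6 | 5.6 |
| 0.01 | 8.2 | 9.8 |
| 0.02 | 13.1 | 15.3 |
| 0.03 | 15.8 | 18.0 |
| 0.05 | 17.6 | 19.3 |
| 0.1 | 14.9 | 15.4 |
| 0.2 | 9.1 | 9.2 |

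**Sensitivity.**
- If deaths stop after Day 28, the gaps at h = 0.02 are 12.7 and 14.6 points.
- If deaths come early (mean 7 days among those who die), the largest gap over all h is 24 to 25 points.
- If GC4419 survival is 70%, the gaps at h = 0.02 are 6.7 and 7.8 points. If survival is equal, they are zero.

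**Harmful drug.** Take 30% survival on GC4419 (m = 0.0430), h = 0.02, T = 42. Non-fatal incidence is 0.02/0.0630 × (1 − e^(−2.646)) = 29.5%, against 37.9% on placebo.

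**Rows that count deaths.** Treat h as a serious-event hazard and count every death as an SAE. Incidence is then 1 − e^(−(h+m)T). At h = 0.02 and T = 42 this is 85% on placebo, 63% on GC4419 at 90% survival, and 93% on GC4419 at 30% survival. This row moves opposite to the non-fatal row.

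**Candidate remedies.**
- Fixed window to Day 8, h = 0.02: 14.6% against 13.4%, so about 1 point remains.
- One pooled rate per subject-day alive and event-free: exact if h is constant, biased if events cluster early. With h = 0.05 to Day 14 and 0.005 after, in both arms, first events per subject over event-free days alive to Day 42 are 0.550/21.53 on GC4419 and 0.467/15.35 on placebo. These are 2.56 and 3.04 per 100 days, a ratio of 0.84 where the truth is 1.
- The same hazards split at Days 8 and 28: the ratio is 1.00 in the first and last periods. In the middle period it is (0.1978/9.542)/(0.1530/6.679) = 0.90, because the hazard changes inside that period. Splitting removes most of the bias, and all of it when the cuts match the change.

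**The case against.** Several objections carry weight.

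- **The rates are not predictions.** The documents give no AE hazard, and 50% against 90% is the alternative hypothesis used for power. A reader might take 13 to 15 points as the excess to expect; the documents do not support that. For an AE seen in about 10% of placebo subjects the gap is only 4 to 5 points, and under equal survival it vanishes.
- **The SAP is not available.** A reader might infer that no adjustment is planned. All that can be said is that none is stated in Section 11.6.
- **A lethal drug would not simply look safer.** A reader might infer this from the harmful-drug case, but it holds only for non-fatal AE tables. Death is the primary endpoint, is listed under Section 11.6 and meets the SAE definition in Section 10.4.2. Section 10.5.1 lets investigators report natural disease progression as a non-serious AE, so how many deaths would reach the SAE row is uncertain.
- **The practical effect is limited.** Section 9.1 anticipates infusion-related toxicity that resolves within 1 to 2 hours, so drug effects should appear mostly in the dosing week, where the bias is small. A gap of 49.2% against 36.2% has a 95% half-width of 1.96·√((0.492·0.508 + 0.362·0.638)/25), or about 27 points. No stated test or numerical rule uses the crude difference.

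These points limit the size and urgency of the problem. They do not remove it: the stated measure still confounds toxicity with survival, in opposite directions for fatal and non-fatal events.

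**Conclusion.** The point stands as a recommended improvement to the safety tables; it does not threaten the primary analysis. With equal non-fatal AE hazards, the Section 11.6 measure gives a spurious excess on GC4419 of 13 points (Day 37) to 15 points (Day 42) at an assumed 2% per day and the powering survival rates. Across hazards of 0.005 to 0.05 per day the excess is about 5 to 19 points. These sizes assume constant hazards and would shrink to zero with equal survival.

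If GC4419 raised mortality to 70%, the non-fatal tables would understate its risk (29.5% against 37.9%), while a row counting every death as an SAE would show the harm (93% against 85%). The direction of the bias therefore depends on whether a row includes deaths, and the stated tables do not separate the two.

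**What to change.** In Section 11.6 or the SAP, for both the final and the DMC tables, keep the crude full-window incidence and add:

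1. AE and SAE incidence by arm in a fixed window from first dose to Day 8 for every dosed subject, whatever dosing was actually received. This sits beside the full-window table and does not replace it, so the post-dosing follow-up keeps its place.
2. Fatal and non-fatal events in separate rows.
3. For the full window, first events per 100 subject-days alive and event-free, by arm and by period (for example Day 1-8, Day 9-28, after Day 28). Give rate ratios and 95% CIs from the period-specific or period-stratified rates. Do not rely on one pooled rate, and use narrower periods if events cluster within one.

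A cumulative incidence curve with death as a competing event is not a substitute: with complete follow-up it returns the same crude percentage.

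The cost is SAP wording and extra tables built from AE dates already collected and death dates needed for the primary endpoint. The downside is longer safety output and wide intervals with 25 per arm, so the tables should be labelled descriptive.
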